Assessment visit 1 will take place prior to TMS treatment. Information will be collected on demographics and a history of substance use and medical conditions. Subjects will be screened using the MINI International Neuropsychiatric Interview to ensure they do not have mental health conditions that should lead to exclusion. This may be conducted remotely by a psychiatrist investigator using a HIPAA compliant Zoom meeting if a psychiatrist is not available to perform the MINI on-site. The subject will complete all assessment surveys. They will also complete several psychological tests, including a Flanker task administered with an iPad, and a digitally administered delay discounting task. They will also submit a urine drug screen if there is not a recent result on file in their EHR, or one is not known to be planned for that day. Then they will complete fMRI imaging. This visit should take 3-4 hours. If the subject elects to participate in the optional EEG and timing task, this will add about an hour to this visit. If they elect to participate in this optional EEG and task, investigators will adhere electroencephalogram (EEG) leads to their scalp and then have them perform 2 blocks of the interval timing task where they estimate the passage of a specified (3 or 12 second) passage of time (~22min - 11 min blocks). The beginning of the trial is indicated by the presentation of either a 3 or a 12 on the computer screen which also indicates the duration of time the subject should estimate. During performance, we will collect electroencephalographic data from patients which will be analyzed offline. Within a week of this visit, the subject will begin TMS treatment. TMS treatment could start as early as the same day if the subject prefers and the schedule allows.

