TMS treatment using theta burst stimulation will be provided 5 days in the first week, five days in the second week, and three times per week in weeks 3 and 4. The start day will be somewhat flexible. Subjects will participate in 5 treatment sessions in each of the first two 7-day periods, and three treatment sessions in each of the third and fourth 7-day periods (treatment weeks). Theta burst stimulation can be completed in as little as 3 minutes per treatment (two sites), so these visits should take roughly 15-20 minutes total when once-weekly additional assessments are not being completed. We will measure blood pressure and pulse prior to each treatment. If systolic blood pressure exceeds 160 mmHg, diastolic blood pressure exceeds 100 mmHg, or pulse exceeds 110 beats per minute, then we will confirm this with a second measurement. If it is confirmed by a second measurement, then the treatment will be withheld, and a clinician contacted to assess the patient. Before each treatment, we will also ask the subject when they last used methamphetamine. Treatment may be withheld if it is too recent to minimize risk of adverse effects, particularly seizure. Participants will be asked to report craving using a single question before and after each treatment. Participants will only be asked to report any adverse event experiences at these visits.

On the last day of TMS in each treatment week when TMS is administered, the subject will be asked to complete additional assessments. At 1 week, 2 weeks, and 3 weeks, these will involve completion of surveys. At weeks 1 and 3 only the Brief Substance Craving Scale will be administered, while additional survey instruments will be administered after week 2. These visits will also involve reporting of the number of days in the last week in which they used methamphetamine as well as whether they remain engaged in a psychosocial treatment and what treatments (partial hospitalization, intensive outpatient, outpatient medical, outpatient psychotherapy, group therapy, other, none). If they were engaged in partial hospitalization or intensive outpatient treatment, we will ask whether they completed the planned course of treatment or stopped early.

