This is a pilot study without an untreated control group so will not be able to establish that the treatment is causal in improving outcomes. The overarching goal is to evaluate the ability to recruit and retain subjects, establish safety of the intervention in this population, evaluate target engagement of TMS using fMRI, and to determine the extent to which patient symptoms and substance use appear to improve during participation in treatment. We anticipate approximately 20 subjects, which should be adequate to statistically detect clinically meaningful changes in symptoms and other outcome measures, depending on attrition. We will randomize order of treatments to gather preliminary data on any differences, but do not anticipate power to detect significant differences in effect by order of treatment with this sample size.

Outcomes

Primary outcomes:

1. Retention in the Study: Measured from Baseline to 12 weeks
2. Retention in Psychosocial Treatment: Measured from Baseline to 18 days (self-reported)

Secondary outcomes (used all available data points as specified in figure 2):

1. Functional Connectivity of the Dorsolateral Prefrontal Cortex and Anterior Insula—change from baseline to 4 weeks. Measured by correlation of region activity over MRI time series data, averaged for left and right hemisphere.
2. Functional Connectivity Dorsolateral Prefrontal Cortex and Anterior Cingulate Cortex—change from baseline to 4 weeks. Measured by correlation of region activity over MRI time series data, averaged for left and right hemisphere.
3. Functional Connectivity of the Medial Prefrontal Cortex and Ventral Striatum—change from baseline to 4 weeks. Measured by correlation of region activity over MRI time series data, averaged for left and right hemisphere.
4. Kirby Delay Discounting Questionnaire, 27 Item

5. Number of Days of Methamphetamine Use in the Past Week
6. Urine Drug Screen Positive for Stimulant
7. Brief Substance Craving Scale
8. Brief Addiction Monitor—Use Subscale
9. Brief Addiction Monitor—Risk Factors Subscale
10. Brief Addiction Monitor—Protective Factors Subscale
11. Brief Addiction Monitor—Satisfaction with Progress Toward Achieving Recovery Goals (question 17)
12. Quality of Life Enjoyment and Satisfaction Questionnaire—Short Form
13. Patient Health Questionnaire--8 Item Scale
14. Generalized Anxiety Disorder 7-item Scale
15. Assessment of Recovery Capital
16. Positive and Negative Affect Scale—Positive Affect Score

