17. Positive and Negative Affect Scale—Negative Affect Score
18. Pittsburgh Sleep Quality Index
19. Difficulties in Emotion Regulation Scale--Short Form
20. UPPS-P Impulsive Behavior Scale, 59-item Revised Version

Safety outcomes

Adverse events are reported at each TMS treatment visit, or if otherwise volunteered by subject.

Populations to be analyzed

Intention to treat: Subjects will be analyzed in the groups they were randomized to. However, only complete data will be used, and subjects were discontinued from the study if they missed more than 4 TMS treatments.

Analyses

Descriptive statistics will be examined for demographic and other variables, overall and by intervention group.

For other analyses, a fixed time will be assigned for each study visit, which approximates the time at which the visit would have occurred on a typical study schedule.

Primary outcomes

The primary analysis will compare intervention groups (DLPFC first or MPFC first) on time to discontinuation in the study and time to discontinuation of psychosocial treatment. The latter is defined as a participant indicating they are no longer in or seeking treatment. All subjects were in treatment or planning treatment at baseline, as an inclusion criterion. Time retained in the study or treatment will be described using Kaplan-Meier curves, and intervention groups will be compared using log-rank tests.

Secondary outcomes

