Most secondary outcomes will be examined using linear mixed models. These allow for estimation of within group change over time as well as between group differences in change over time. Group by continuous time interaction terms will be the primary test of hypotheses for differences between groups. For outcomes measured at only two time points (baseline and week 4), if sample size is not adequate or mixed models do not converge, changes from baseline to the second measure will be calculated. Wilcoxon-rank sum tests or t-tests comparing differences in changes from baseline to week 4 will be used to compare groups, as appropriate based on the data distribution. A generalized estimating equations model clustered on subject with a logit link, with empirical standard error estimates, will be used to analyze the outcome of positive urine drug screens for stimulants, as this is binary, and this approach does not assume a correlation structure. The primary analysis of this outcome will still use a group by continuous time interaction to examine whether the odds of a positive urine drug screen decreases over time in each group, and whether any reduction over time differs between groups.

Missing data

As this is a pilot study with a small sample size, and dropout is expected, analyses will use all available data as feasible for randomized subjects who received at least one treatment, irrespective of the number of data points collected. For changes in functional connectivity as measured by MRI, only subjects with both baseline and 4-week assessments will be included. No imputation of data will be performed.

References

1. Governor's Office of Drug Control Policy. News Release - Iowa Drug Control Report: Life-Changing Progress Amid Evolving Threats.
<https://odcp.iowa.gov/news-release-iowa-drug-control-report-life-changing-progress-amid-evolving-threats>. Published 2019. Updated November 13, 2019. Accessed December 13, 2019, 2019.
2. Iowa Department of Public Health. Substance Abuse Brief, December 2018, Issue 7.
https://idph.iowa.gov/Portals/1/userfiles/133/IASubAbuseBriefNewsletterDec2018_Final.pdf. Published 2018. Accessed December 13, 2019, 2019.

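### Psychosocial retention counts a stop only if the participant reports it, and the SAP has no rule or sensitivity analysis for those who leave without reporting

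*Combined protocol and SAP*

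**What the plan says.** The SAP lists two primary outcomes: retention in the study to 12 weeks, and self-reported retention in psychosocial treatment to 18 days. Under Analyses, Primary outcomes, the event for the second is defined thus: "The latter is defined as a participant indicating they are no longer in or seeking treatment". The method for both is given in one sentence: "Time retained in the study or treatment will be described using Kaplan-Meier curves, and intervention groups will be compared using log-rank tests". No censoring rule accompanies it.

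Study Procedures and Figure 2 place the status question at the scheduled assessments, where participants report "whether they remain engaged in a psychosocial treatment and what treatments". On the example schedule, counting the first TMS day as day 0, the first three weekly assessments fall at about days 4, 11 and 18.

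Two further provisions bear on people who leave. Under Populations to be analyzed, "subjects were discontinued from the study if they missed more than 4 TMS treatments". Under Missing data, the SAP says that dropout is expected and that "No imputation of data will be performed". The section on contacting subjects lost to follow-up allows up to five calls or texts and then a secondary contact, but does not list treatment status among the things to ask.

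**The concern.** An event needs a report, and a person who has gone silent gives none. Whatever happened to that person's treatment, the curve cannot record a stop. Kaplan-Meier censoring then credits silent leavers with the same later risk of stopping as those still attending.

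That assumption needs a defence here. The Significance section describes poor treatment retention and high relapse in this disorder. Recruitment draws partly on the same kinds of programmes whose attendance is being measured, so leaving care and leaving the study may coincide.

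Recruitment and retention are the first aims named in the Sample Size Justification, and the protocol says that feasibility together with improvement would justify a randomized controlled trial. If the two kinds of leaving are linked, worse study retention makes the psychosocial figure err more in the favourable direction. Without a count of unknown statuses, a reader cannot tell by how much.

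**Working it through.** **No figure to reproduce.** The documents give no expected retention, event rate or dropout rate. From the documents: about 20 subjects; status reported at about days 4, 11 and 18; Kaplan-Meier; no imputation. Every rate below is an assumption.

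**1. A trial of 20 by hand.** Suppose two participants report stopping (one at day 11, one at day 18) and four leave silently: two before day 4, one before day 11 and one before day 18. The numbers at risk are 18, 17 and 15.

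Kaplan-Meier at day 18 = (18/18) × (16/17) × (14/15) = 87.8%.

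True retention depends on how many of the four had stopped:
- none: 18/20 = 90%
- one: 17/20 = 85%
- two: 16/20 = 80%
- all four: 14/20 = 70%

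The same observed data fit any of these.

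**2. Expected size of the error.** Let L be the share leaving silently by day 18, q the share of leavers who have stopped treatment, and 5% the share of stayers who stop and report it. Leavers and reported stops are spread evenly over the three visits.

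True retention = (1 − L) × 0.95 + L × (1 − q).

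For L = 20% and q = 50%: 0.80 × 0.95 + 0.20 × 0.50 = 86%.

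For Kaplan-Meier, 0.20/3 of the sample is lost before each visit and 0.80 × 0.05/3 = 0.0133 reports stopping at each. The shares at risk are 0.9333, 0.8533 and 0.7733, so the estimate is 0.9857 × 0.9844 × 0.9828 = 95.4%. The overstatement is 9.4 points.

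Overstatement in percentage points over a wider range:

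| Share leaving (Kaplan-Meier) | q = 5% | q = 15% | q = 30% | q = 50% | q = 80% |
|---|---|---|---|---|---|
| 10% (95.2%) | 0.2 | 1.2 | 2.7 | 4.7 | 7.7 |
| 20% (95.4%) | 0.4 | 2.4 | 5.4 | 9.4 | 15.4 |
| 30% (95.6%) | 0.6 | 3.6 | 8.1 | 14.1 | 23.1 |
| 40% (95.8%) | 0.8 | 4.8 | 10.8 | 18.8 | 30.8 |

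The first column is the case of no link: leavers stop at the stayers' rate and the error stays under 1 point.

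**3. Chance in a single trial.** Simulating trials of 20 with q = 50%, the gap is 10 points or more in about 46% of trials at 20% leaving and about 70% at 30% leaving.

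**4. Does the direction always hold?** A separate large simulation let participants stop treatment with probability 5% per visit, with 28% to 35% dropping out in total:
- Dropout unrelated to stopping: 85.8% against a true 85.7%.
- Those who stop drop out more often (40% against 9% per visit): 90.3% against 85.7%.
- Everyone who stops leaves unreported: 100% against 85.8%.
- Those who stop never drop out: 83.9% against 85.8%, a slight understatement.

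**5. Does the unstated rule matter?** Take L = 20% and q = 50%, with truth 86%. Censoring gives 95.4%. Excluding leavers gives 95%, the stayers' rate. Treating them as retained gives 1 − 0.80 × 0.05 = 96%. Counting them all as events gives 0.80 × 0.95 = 76%. The first three agree closely and all miss in the same direction; the last is a lower bound.

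**The case against.** A reader might infer that anyone who leaves the study can never be an event. The documents do not say so. A participant who reports stopping and then leaves is an event, and so may be one who is reached again and says so. Only those who leave without reporting are missed. Re-contact is a weak safeguard as written, though: treatment status is not among its listed questions, and five contacts two days apart span at least 4 × 2 = 8 days, so attempts starting at day 11 run past day 18.

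A reader might also infer that retention is overstated as a matter of fact. That needs two things the documents do not supply: that leavers are censored, which Kaplan-Meier only implies, and that leavers stop treatment more often than stayers. With no link the error is under 1 point, and with the opposite link it reverses slightly. The large figures come from assuming that leavers stop 6 to 16 times as often as stayers (30% to 80% against 5%). This objection stands in full, and the point is therefore conditional.

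Study retention is the other primary outcome with its own curve, so heavy dropout would be visible, and no go/no-go threshold is set on psychosocial retention. Both lessen the harm. But the study-retention curve does not show how many statuses were unknown at day 18.

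Bias in the log-rank comparison adds little. It needs dropout to differ by stimulation order, although both groups receive both stimulations. The SAP also disclaims power for order: with 4 to 8 events and a hazard ratio of 3, power is about 20% to 34%.

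**Conclusion.** The concern holds in conditional form. As written, a participant who leaves without reporting is not counted as having stopped treatment, and the SAP neither states how that person is handled nor tests the assumption behind it. If leaving the study is linked to stopping treatment, psychosocial retention is overstated. Under the assumed 5% stopping among stayers, the size runs from under 1 point with no link, through about 9 points at 20% leaving with half having stopped, to about 31 points at 40% leaving with 80% having stopped. The documents make a link plausible but give no rate for either part of it, so neither the presence nor the size of the bias is established. What matters is the retention estimate, not the comparison between orders. This is a should-fix clarification and a cheap one.

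**What to change.** In the SAP, under Analyses, Primary outcomes:
1. State that in the main curve a participant with no further status report is censored at the last report.
2. Report by arm the number who left with unknown treatment status by day 18.
3. Prespecify a sensitivity curve in which each such participant counts as discontinued at the next scheduled weekly assessment. Show it beside the main curve and label it a conservative lower bound. It will understate retention whenever leavers remain in treatment, so it should not replace the main figure.

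In the procedures for contacting subjects lost to follow-up, add a question to the participant on current psychosocial treatment and, if it has stopped, when.

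A look-up in the EHR is optional where a record is available. The study already checks it for urine results ("if there is not a recent result on file in their EHR"). However, the documents mention no access to programme records, and participants recruited by advertising may be treated elsewhere.

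The cost is some SAP wording, one extra analysis, one added question at re-contact, and a less favourable lower-bound figure in the report.

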Screening questions that warrant follow up if the participant answers "yes":

- Have you been diagnosed with a methamphetamine use disorder? (follow up- providers to determine if participant should have a methamphetamine use diagnosis, if not currently diagnosed)
- Are you claustrophobic or afraid of small, closed-in spaces? (follow-up- participant needs to confirm that they can handle being in an MRI machine through additional questions)
- Do you have a problem with loud noises? (follow-up- participant needs to confirm that the noises from the MRI are not too loud through additional questions)
- Have you ever had a neurosurgical procedure? (follow up- type of procedure matters)
- Have you been diagnosed with another neurological disorder? (follow-up- type of disorder matters)
- Are you able to make it to all visits for this study without assistance?
Additional information: This involves a baseline visit, then visits five days a week for two weeks and three days a week for two more weeks. The visits need to take place Monday through Friday, but we can start most any day depending on what's convenient for you. There will also be follow-up visits that can be completed by phone or in person one month and two months after the other visits are completed.
 - If not, Please explain any additional services you may need to get to and from study appointments, (i.e. transportation)

Randomization

The randomization scheme was block randomization stratified by study site, with block sizes of 4 and a 1:1 ratio, designed to ensure approximate balance in the number of subjects. Subjects are randomized to receive stimulation at the DLPFC or MPFC first, although both groups receive stimulation at both sites at each visit. The subject is assigned to a group at the first TMS treatment visit.

Intervention

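### The urine-screen GEE uses uncorrected empirical standard errors with about 20 subjects and names neither test nor working correlation: Wald tests would be moderately liberal with weekly screens, and the within-group trend is open to dropout bias.

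*Combined protocol and SAP*

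**What the plan says.** SAP, Secondary outcomes: "A generalized estimating equations model clustered on subject with a logit link, with empirical standard error estimates, will be used to analyze the outcome" of a stimulant-positive urine screen. Part of the reason given is that "this approach does not assume a correlation structure". The model is to "examine whether the odds of a positive urine drug screen decreases over time in each group" and, through a group-by-continuous-time term, whether the change differs by order group. No test statistic, reference distribution, small-sample correction or alpha is given.

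Sample Size Justification: "We anticipate approximately 20 subjects". Randomization is "with block sizes of 4 and a 1:1 ratio", so about 10 per order group. The SAP disclaims power for the order comparison.

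The number of screens per subject is unclear. The SAP's Outcomes section says that secondary outcomes "used all available data points as specified in figure 2". Figure 2 marks a screen, where needed, at the first visit and at the end of each of weeks 1 to 4, and Figure 1 agrees. The Study Procedures text describes one at baseline ("They will also submit a urine drug screen if there is not a recent result on file in their EHR") and another after week 4. For weeks 1 to 3 it describes surveys and self-report only.

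The data rule is also unclear. Populations to be analyzed restricts the analysis to complete data. Missing data uses whatever is available from treated randomized subjects, expects dropout and rules out imputation.

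**The concern.** The empirical (sandwich) variance is a large-sample result in the number of subjects. With few subjects, fitting the model shrinks the residuals, the variance tends to be too small, and a normal reference is too narrow. The interaction here rests on about 20 clusters and each within-group slope on about 10, before attrition.

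The second issue is separate. Every GEE has a working correlation. If it is independence, empirical standard errors protect the variance against a wrong correlation, but they do not protect the estimate. Early screens come from everyone and later screens from those who stay. If users leave more often, the share positive falls although nobody's use has changed.

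The within-group trend is the result most likely to be read as benefit, because power by order is disclaimed. This is also the drug-use outcome that is not self-reported, and Potential Benefits to Society names improvement in substance use among the grounds for a randomized trial.

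**Working it through.** **1. Inputs.** From the documents: about 20 subjects, 1:1 allocation, logit GEE, empirical standard errors, two or five screens. Assumed, because the documents give no figure: two-sided 5% level, Wald z test, working independence, constant positivity of 50%-85%, subject SD 2 on the logit scale, loss unrelated to use of 0% or 12% per visit. The plan gives no size or power figure to reproduce.

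**2. Reference distribution alone.** P(|t| > 1.96) is 6.6% on 18 df and 8.2% on 9 df. So some excess over 5% is expected at 20 subjects in all and 10 per group.

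**3. Simulated size.** Model with an intercept and slope per group and no true change; 4,000 trials per scenario (Monte Carlo SE √(0.05 × 0.95 / 4,000) = 0.34 points). Rejection at nominal 5%, plain empirical standard error, Wald z:

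| Screens | Positive | Interaction | Within-group slope |
|---|---|---|---|
| Five | 50%-65% | 7.1%-8.6% | 8.4%-9.4% |
| Five | 75% | 9.4%-11.0% | 10.6%-12.7% |
| Five | 85% | 15.8%-16.6% | 18.1%-19.9% |
| Half of weeks 1-3 | 50%-65% | 7.2%-9.2% | 7.7%-9.5% |
| Two | 50%-65% | 3.5%-6.3% | 2.5%-5.4% |

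A simulation that set the within-subject correlation directly (0.3 or 0.6) agreed: 6.1%-11.4% and 6.5%-11.6% with five screens at 30%-70% positive, and no clear excess with two. The problem with two screens is different. At 75% positive the interaction could not be estimated in 18.5%-42.2% of trials, against 0.3%-1.5% with five.

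**4. Other tests on the same data.** A generalized score test of the interaction, which also uses the empirical variance, rejected in 4.4%-6.1% with five screens, including at 85% positive. A Kauermann-Carroll corrected sandwich with t on 20 − 4 = 16 df gave 4.7%-5.9% for the slope at 50%-65% positive, but 7.1%-8.2% at 75% and 13.8%-14.8% at 85%. With two screens at 50%-65% it gave 0.6%-2.5% for the slope, which is conservative.

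**5. Dropout bias under independence.** Let q1 and q0 be the loss per visit for a positive and a negative. If each subject's result never changed, the odds of a positive among those remaining would be multiplied by (1 − q1)/(1 − q0) at each visit. Over four visits, with q0 = 5%:
- q1 = 10%: (0.90/0.95)⁴ = 0.81
- q1 = 15%: (0.85/0.95)⁴ = 0.64
- q1 = 25%: (0.75/0.95)⁴ = 0.39

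Results that vary within subject soften this. Solving the estimating equations over all screen and dropout patterns with SD 2 gives:

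| Loss after a positive | Retained at week 4 | 4-week OR (true value 1) |
|---|---|---|
| 10% | 68%-73% | 0.89-0.93 |
| 15% | 56%-66% | 0.79-0.86 |
| 25% | 38%-54% | 0.60-0.72 |

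The upper end of each OR range applies if loss follows the previous result, the lower end if it follows the unseen current one. Two screens give the same ORs within 0.01. If only subjects with complete data were analysed, the direction would not be fixed: 1.03-1.16 for loss after the previous result, 0.86-0.97 for loss after the current one.

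**6. Exchangeable working correlation.** With five screens, random-intercept data and loss following an observed screen, the OR is close to 1 (1.00-1.07). If loss follows the unseen current result it stays at 0.94, 0.87-0.88 or 0.75 for the three loss rates. With correlation that decays over time, loss tied to observed screens gave 1.04-1.16, a false increase.

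**The case against.** The size figures presuppose a Wald z test that the SAP does not name. A score test fits the same wording and is near nominal for the interaction. This stands, so the excess is conditional on the test. It does not dispose of the point, because the SAP leaves the choice open and the within-group slopes were not checked under a score test.

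On the schedule in the Study Procedures text, with two screens, the plan as written shows no material excess and a corrected sandwich would make it conservative. This stands too, and it is why the schedule must be settled before any correction is chosen.

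Loss tied to drug use is an assumption. The protocol allows treatment to be withheld after recent use, and the SAP discontinues subjects who miss more than four treatments, but the documents do not say that withheld sessions count as missed. The link is plausible and not established.

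On non-estimable slopes, the SAP has a fallback ("if sample size is not adequate or mixed models do not converge"). It can be argued that this covers two-screen data, although the comparison of changes it describes suits a continuous measure better than a binary one.

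Finally, this is one of 20 secondary outcomes in an uncontrolled pilot that disclaims causal conclusions, and the retention curves will show the dropout. That limits the weight.

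**Conclusion.** The concern holds in conditional form, with minor to moderate weight. If week 1-3 screens are taken and Wald z tests are used, the urine-screen tests are moderately liberal at 50%-65% positive and clearly so at 85%. Whichever schedule applies, the stated rationale about correlation is inaccurate. If all available data are used under independence and users are lost more often, the within-group trend is biased towards decline. The rates, the SD, the level and the test are assumptions.

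A reader might infer three stronger things that the documents do not support:
- That the planned tests are too liberal in any case. This depends on a test and a number of screens that the documents leave open.
- That the order comparison is biased by dropout. It is not systematically shifted if loss acts equally in both groups, and nothing in the documents says that it would not.
- That naming an exchangeable correlation cures the dropout problem. It helps only for loss tied to observed screens, and it can overshoot.

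**What to change.** 1. First reconcile the passages. State whether week 1-3 screens are taken (Study Procedures text against Figures 1 and 2), and whether the analysis uses complete data only or all available data (Populations to be analyzed against Missing data).
2. Name the tests. Use a generalized score test for the interaction. With five screens, give the within-group slopes and their intervals a Kauermann-Carroll corrected sandwich and a t reference on subjects minus four, and state that this does not restore size when positives are very common. Do not apply it by default with two screens.
3. Delete the statement that no correlation structure is assumed and name the working correlation. Report the within-group trend under both independence and exchangeable, with the limits of the latter stated.
4. Report the screens obtained by visit and order group, and the baseline result in those lost and those retained. This needs no imputation.

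The cost is SAP wording and a few lines of code. With five screens at 20 subjects, the corrected 95% intervals are about 14%-16% wider; if only 14 subjects contribute, 23%-28%.
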